8.7 Daily Treatment Duration

The LCIG pump start time and end time at each clinic visit will be recorded on the Study Drug Prescription eCRF. Daily treatment duration (hours of pump operation) will be summarized with descriptive statistics (mean, standard deviation, median, minimum and maximum duration) at each visit.

8.8 Tube Replacements

The number and percentage of LCIG subjects with each specific count of PEG-J tube replacements will be summarized as well as the number and percentage of LCIG subjects with one or more replacements. The number of PEG-J tube replacements will also be summarized by descriptive statistics. The time to the first PEG-J tube replacement will also be estimated using Kaplan-Meier methodology. For the Kaplan-Meier analysis, subjects who did not have a PEG-J tube replacement during the study will be censored at the end of their Study M12-927 PEG-J tube exposure. Subjects with a PEG-J tube removal after their last infusion of Study M12-927 study drug will be censored at this final tube removal date. Subjects without a PEG-J tube removal after their last infusion of Study M12-927 study drug will be censored on the date of their final participation in Study M12-927 (last contact or visit date).

9.0 Efficacy and Health Outcome Analysis

9.1 General Considerations

This is a randomized open-label study. Unless otherwise specified, statistical tests will be two-sided and the null hypothesis will be rejected at the significance level of $\alpha = 0.050$. *P* values will be rounded to 3 decimal places before assessing statistical significance. Unless noted otherwise, all analyses will be performed with the Intent-to-Treat Dataset. Missing data will not be imputed unless otherwise specified.

9.2 Primary Efficacy Analysis

NMSS Total Score

The NMSS was developed to assess non-motor symptoms in PD. It is obtained by interview and rated by health professionals. It contains 30 questions grouped into 9 domains as follows.

NMSS Domain	Number of Questions	Score Range
Cardiovascular including falls	2	0 – 24
Sleep/fatigue	4	0 – 48
Mood/cognition	6	0 – 72
Perceptual problems/hallucinations	3	0 – 36
Attention/memory	3	0 – 36
Gastrointestinal tract	3	0 – 36
Urinary	3	0 – 36
Sexual function	2	0 – 24
Miscellaneous	4	0 – 48

Each question is scored with respect to severity and frequency. Severity is rated on a scale where 0 = none, 1 = mild, 2 = moderate and 3 = severe. Frequency is rated on a scale where 1 = rarely, 2 = often, 3 = frequent, and 4 = very frequent. Item scores are calculated as the product of severity and frequency. Domain scores and a total score are obtained by summing the item scores. The NMSS total score ranges from 0 to 360. There is no imputation of missing responses. If one or more item scores are missing, the total score and respective domain score will not be calculated.

PDSS-2 Total Score

The PDSS-2 was developed from the PDSS based upon the need for a treatment-measuring tool containing PD-specific sleep disorders. The instrument was extended to address specific sleep disturbances such as restless leg syndrome (RLS), morning akinesia, pain, and sleep apnea. The frequency is assessed for the 15 sleep problems based on a 5-point Likert-type scale (ranging from 0 [never] to 4 [very often]). Scores are

calculated for each of the 3 domains (motor symptoms at night, PD symptoms at night, and disturbed sleep) as well as a total score. The PDSS-2 domain scores range from 0 to 20 and the total score ranges from 0 to 60. There is no imputation of missing responses. If one or more item scores are missing, the total score and respective domain score will not be calculated.

The primary efficacy variables will be the change from baseline to Week 26 in the NMSS and PDSS-2 total scores. They will each be estimated using PROC MIXED and a mixed-effect repeated measures model (MMRM) for the change from baseline to each scheduled visit. The model will include the fixed effects of treatment, country and visit, with baseline score as a covariate, and the baseline score-by-visit interaction. The unstructured covariance structure will be used to estimate the within subject variance-covariance structure and Satterthwaite's approximation will be used to estimate the denominator degrees of freedom. If the model fails to converge, the first order autoregressive (AR[1]) covariance structure will be substituted. If the model still fails to converge, the compound symmetry (CS) covariance structure will be substituted. Type III sum-of-squares and least-square (LS) means will be used for statistical evaluations. The LS mean and 95% confidence interval obtained from the model will be presented. The primary comparison will be the contrast between LCIG and optimized medical treatment at the Week 26 Visit. The primary null and alternative hypotheses may be expressed as:

$$H_0: \mu_{\text{LCIG}} = \mu_{\text{OMT}}$$

$$H_A: \mu_{\text{LCIG}} \neq \mu_{\text{OMT}}$$

Where μ_{LCIG} is the mean change from baseline to Week 26 for LCIG group in the NMSS (or PDSS-2) total score and μ_{OMT} is the mean change from baseline to Week 26 for OMT group in the NMSS (or PDSS-2) total score. The statistical tests at other visits will be considered secondary.

The change in the NMSS (or PDSS-2) total score to each planned visit and to the final visit will also be summarized by the following descriptive statistics: number of non-

missing observations, mean baseline score and standard deviation, mean visit score and standard deviation, median visit score and range, mean change from baseline and its standard deviation and standard error, median change from baseline and range. The hypothesis of change from baseline will be evaluated at each visit with a one-sample t-test.

The two-sided P values obtained from the MMRM model for NMSS total score change from baseline to Week 26 and PDSS-2 total score change from baseline to Week 26 will be adjusted for multiplicity using the Hochberg procedure. This method controls the family-wise error rate (FWER) at a pre-specified significance level ($\alpha = 0.05$). Specifically, the following steps will be followed:

- If the larger of the 2 P values is ≤ 0.05 (i.e., both P values are ≤ 0.05), both primary endpoints are considered statistically significant.
- If the larger of the 2 P value is > 0.05 , then compare the smaller P value with 0.025. The second primary endpoint is statistically significant if the P value is ≤ 0.025 ; otherwise, neither primary endpoint is considered statistically significant.

The mean NMSS and PDSS-2 total scores at baseline, Week 6, Week 12 and Week 26 and the mean changes in NMSS and PDSS-2 total scores from baseline to Week 6, Week 12 and Week 26 will be summarized by domain. Each mean domain score as well as the percentage it represents of the NMSS and PDSS-2 total score will be presented.

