8.1.3.1 Primary Efficacy Analysis

There are 2 alternative primary efficacy variables, change from baseline to Week 26 for NMSS total score and change from baseline to Week 26 for PDSS-2 total score. Either variable considered statistically significant after multiplicity adjustment is sufficient to declare success of the study.

NMSS Total Score

The NMSS was developed to assess non-motor symptoms in PD. It is obtained through interview and rated by health professionals. It contains 30 questions grouped into 9 domains: cardiovascular (2 items), sleep/fatigue (4 items), mood/cognition (6 items), perceptual problems/hallucinations (3 items), attention/memory (3 items), gastrointestinal tract (3 items), urinary (3 items), sexual function (2 items), and miscellaneous (4 items). Each question is scored with respect to severity and frequency. Severity is rated on a

scale where 0 = none, 1 = mild, 2 = moderate and 3 = severe. Frequency is rated on a scale where 1 = rarely, 2 = often, 3 = frequent and 4 = very frequent. Item scores are calculated as the product of severity and frequency. Domain scores and a total score are obtained by summing the item scores.

PDSS-2 Total Score

The PDSS-2 was developed from the PDSS based upon the need for a treatment-measuring tool containing PD-specific sleep disorders. The instrument was extended to address specific sleep disturbances such as RLS, akinesia, pain, and sleep apnea. The frequency is assessed for the 15 sleep problems based on a 5-point Likert-type scale (ranging from 0 [never] to 4 [very often]). Scores are calculated for each domain as well as a total score.

Primary Analysis Model and Multiplicity Adjustment

The primary efficacy analysis model is a likelihood-based mixed-effects model repeated measures (MMRM) analysis of the change from baseline for each post-baseline observation using all observed data. The model will include fixed, categorical effects for treatment, country, visit, and treatment-by-visit interaction, with continuous fixed covariates for baseline score and the baseline score-by-visit interaction. The primary comparison will be the contrast between LCIG and optimized oral treatment at the Week 26 Visit.

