8.2 Determination of Sample Size

Approximately 88 subjects will be enrolled into the study and randomized in a 1:1 ratio to either optimized medical treatment or LCIG. There are no results on NMSS or PDSS-2 available from randomized trials comparing LCIG and OMT. Interim data from ongoing Phase 3b Study M12-920 showed that the improvement in NMSS total score from baseline to Week 12 is 24.8 in the LCIG group with standard deviation of 24. Results from Zibetti et al (2013) showed that the improvement in PDSS-2 total score after an average of 3.5 months of LCIG treatment was 13.1. The standard deviation was not provided and is estimated to be 12.2 assuming the correlation between baseline and follow-up visits is 0.5.

The significance level for this study is 0.05. For sample size determination, it is assumed that the improvement in the OMT group is 33% of the LCIG group, i.e., the improvement is 8.2 on NMSS total score and 4.3 on PDSS-2 total score, and that the correlation between these 2 measures is 0.5. Simulation showed that a study with 37 subjects per group will have 90% power to declare statistical significance on at least one of these 2 alternative primary endpoints after multiplicity adjustment using Hochberg procedure. It is further assumed that 10% of randomized subjects in either treatment group will not provide post-randomization efficacy assessment. Additional simulations showed that 44 subjects per group will provide 90% power in the sensitivity analysis using baseline observation carried forward for subjects without post-randomization assessment. Therefore the total planned enrollment is decided to be 88 subjects.

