4.3 Sample Size

Approximately 88 subjects will be enrolled into the study and randomized in a 1:1 ratio to either optimized medical treatment or LCIG. There are no data on NMSS or PDSS-2 available from randomized trials comparing LCIG and OMT. Interim data from ongoing Phase 3b Study M12-920 showed that the improvement in NMSS total score from baseline to Week 12 is 24.8 in the LCIG group with standard deviation of 24. Results from Zibetti et al (2013) showed that the improvement in PDSS 2 total score after an average of 3.5 months of LCIG treatment was 13.1. The standard deviation was not provided and is estimated to be 12.2 assuming the correlation between baseline and follow-up visits is 0.5.

The significance level for this study is 0.05. For sample size determination, it is assumed that the improvement in the OMT group is 33% of the LCIG group, i.e., the improvement is 8.2 on NMSS total score and 4.3 on PDSS-2 total score, and that the correlation between these 2 measures is 0.5. Simulation showed that a study with 37 subjects per

group will have 90% power to declare statistical significance on at least one of these 2 alternative primary endpoints after multiplicity adjustment using Hochberg procedure. It is further assumed that 10% of randomized subjects in either treatment group will not provide post-randomization efficacy assessment. Additional simulations showed that 44 subjects per group will provide 90% power in the sensitivity analysis using baseline observation carried forward for subjects without post-randomization assessment. Therefore the total planned enrollment is decided to be 88 subjects.

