9.3 Additional Efficacy Analyses

Secondary Analysis of the Primary Efficacy Variables

Analysis of covariance (ANCOVA) analyses will be carried out on change from baseline to final NMSS total score and change from baseline to final PDSS-2 total score. The ANCOVA model will contain treatment and country as the main effects and baseline score as the covariate. Sensitivity analyses will be carried out on the above variables with the same ANCOVA model using all randomized subjects. In this analysis, Baseline

Observation Carried Forward (BLOCF) will be applied to subjects who do not have post-randomization assessment of NMSS or PDSS-2.

Analysis of Secondary Efficacy Variables

The MMRM model, and the descriptive statistic summary described for the NMSS and PDSS-2 total score will also be used to evaluate the change from baseline in each of the following efficacy endpoints:

- UPDRS Part II score
- Parkinson's Disease Questionnaire-8 (PDQ-8) summary index
- NMSS domain scores
- PDSS-2 domain scores
- UPDRS total score, Part I score, Part III score, Part IV score
- Parkinson Anxiety Scale (PAS) total and subscale scores
- Geriatric Depression Scale (GDS-15)
- King's PD Pain Scale total and domain scores

For CGI-C and PGIC, an analysis of variance (ANOVA) model containing treatment and country as the main effects will be carried out.

UPDRS Part II score, CGI-C score and PDQ-8 summary index are key secondary endpoints. If both primary efficacy variables are statistically significant after adjusting for multiplicity, the Stepwise Gatekeeping Procedure will be utilized and the 3 key secondary endpoints will be tested using the Hochberg procedure with significance level of 0.05. Specifically, the following steps will be followed:

- If the largest of the 3 P values is ≤ 0.05 (i.e., all 3 P values are ≤ 0.05), all 3 key secondary endpoints are considered statistically significant.
- If the largest of the 3 P value is > 0.05 , then compare the middle P value with 0.025. The second and third key secondary endpoints are both statistically significant if the middle P value is ≤ 0.025 .

- If the largest of the 3 P value is > 0.05 and the middle P value is > 0.025 , then compare the smallest P value with 0.0167. If the smallest P value is ≤ 0.0167 , then the third key secondary endpoint is statistically significant. Otherwise, none of the 3 key secondary endpoints can be considered statistically significant.

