12.0 Summary of Changes

This SAP contains no change in analysis from the latest version of the protocol (Protocol Amendment 4).

The changes in this SAP from SAP V1.0 is: Per protocol amendments, subjects from South Korean/United States who complete the 26-week clinical study will have the option to enter an extension of the study. This SAP added the description for Extension Period analyses.

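### The SAP's primary MMRM drops the protocol's treatment-by-visit term, so its Week 26 contrast is one treatment effect averaged over Weeks 6, 12 and 26

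*SAP*

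**What the plan says.** Protocol 8.1.3.1 defines the primary MMRM on change from baseline: "The model will include fixed, categorical effects for treatment, country, visit, and treatment-by-visit interaction", with baseline score and baseline-by-visit as covariates. The protocol synopsis also includes treatment-by-visit.

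SAP 9.2 defines the model for the same two endpoints: "The model will include the fixed effects of treatment, country and visit, with baseline score as a covariate, and the baseline score-by-visit interaction". The only interaction named is baseline-by-visit.

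The same SAP section sets the target: "The primary comparison will be the contrast between LCIG and optimized medical treatment at the Week 26 Visit". It writes both hypotheses in terms of mean change from baseline to Week 26 and calls tests at other visits secondary.

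SAP 9.3 extends the model: "The MMRM model, and the descriptive statistic summary described for the NMSS and PDSS-2 total score will also be used" for UPDRS Part II, the PDQ-8 summary index and the other scales. SAP 9.5 refers to the MMRM without restating its terms. SAP 12.0 says: "This SAP contains no change in analysis from the latest version of the protocol".

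**The concern.** A repeated-measures model with treatment and visit as main effects only has a single treatment parameter. The LS-mean difference between arms is then identical at every visit, whichever visit the contrast names. Baseline-by-visit lets the baseline slope vary over time but does not make the treatment effect visit-specific. The SAP therefore asks for a Week 26 contrast, and for separate tests at other visits, from a model that can supply neither.

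At stake are the estimate, standard error and P value for both primary endpoints, and with them the Hochberg decision and the gate to the key secondaries. Two of the three key secondaries use the same model. An effect that grows towards Week 26 would be understated. An effect that fades would be overstated, and the Week 26 null could be rejected when nothing remains at Week 26.

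The design gives no assurance of a constant effect. LCIG dose may be adjusted up to Day 28 (Protocol 5.1.2.2). Other anti-PD drugs are withdrawn at the start and may return only after 28 days. The Week 6 analysis window opens on Study Day 2 (SAP 6.4, Table 1). The planning effects come from Week 12 and from about 3.5 months, not from Week 26.

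**Working it through.** **Inputs from the documents** (Protocol 8.2; SAP 4.3 and 9.1)
- Family-wise alpha 0.05, two-sided.
- NMSS improvement 24.8 (LCIG) and 8.2 (OMT), SD 24: difference 24.8 − 8.2 = 16.6.
- PDSS-2 improvement 13.1 and 4.3, SD 12.2: difference 13.1 − 4.3 = 8.8.
- Correlation between endpoints 0.5; 44 per group; 10% without a post-randomization assessment.

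**Assumptions (not in the documents)**
- 40 analysed per arm (44 × 0.9 = 39.6).
- SD 24 at each visit.
- Between-visit correlation: compound symmetry 0.5, or AR(1) with 0.7.
- The effect profiles over visits.

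**Step 1: the plan's own power.** The protocol's statement is: "a study with 37 subjects per group will have 90% power to declare statistical significance on at least one of these 2 alternative primary endpoints". Simulating two correlated endpoints with t-tests and the Hochberg rule gives 90.5% at 37 per group. With 44 per group and 10% set to zero change it gives 90.6%. Both figures reproduce. They rest on one change score per endpoint, so they do not depend on the MMRM specification.

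**Step 2: what the SAP model estimates.** Let R be the correlation matrix of the three visits. With equal variances, the generalised least squares treatment estimate without the interaction is Σ wᵥ·δᵥ, where δᵥ is the difference at visit v and w = R⁻¹1 / (1′R⁻¹1). The weights for Weeks 6/12/26 are:
- Compound symmetry: 0.33/0.33/0.33.
- AR(1) 0.7: 0.43/0.13/0.43.
- One assumed example with variance rising over time: 0.57/0.28/0.16.

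Week 26 carries less than half the weight in each case. For a build-up of 50%, 75% and 100% of plan, compound symmetry gives 16.6 × (0.50 + 0.75 + 1.00)/3 = 12.45. AR(1) also gives 16.6 × 0.75 = 12.45, because its weights are symmetric.

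**Step 3: standard errors.** With the interaction, SE = 24 × √(2/40) = 5.37. Without it, this is divided by √(1′R⁻¹1). That gives 5.37 × 0.816 = 4.38 (compound symmetry) or 5.37 × 0.860 = 4.62 (AR(1)). The simulated averages were 4.31 and 4.53.

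**Step 4: simulation.** NMSS, 4,000 trials per row, estimated unstructured covariance, baseline slope by visit, two-sided 0.05. Cells show mean estimate and rejection rate.

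| True difference, Weeks 6/12/26 | With treatment-by-visit | SAP model, compound symmetry 0.5 | SAP model, AR(1) 0.7 |
|---|---|---|---|
| 16.6/16.6/16.6 | 16.5–16.6; 85–86% | 16.6; 96% | 16.5; 95% |
| 0/8.3/16.6 | 16.5–16.6; 85–86% | 8.3; 48% | 8.2; 43% |
| 16.6/16.6/8.3 | 8.2–8.3; 32% | 13.7; 87% | 13.0; 79% |
| 16.6/8.3/0 | about 0; 5% | 8.2; 48% | 8.2; 43% |
| 16.6/16.6/0 | about 0; 5% | 10.9; 68% | 9.4; 52% |
| 0/0/0 | about 0; 5% | about 0; 6% | about 0.1; 6% |

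The last row shows that the excess rejections in the two rows above it come from averaging over visits and not from small-sample behaviour of the fit.

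For the milder 50/75/100% build-up, a separate simulation with visit correlations of 0.5 to 0.7 gave an estimate of 12.4 instead of 16.6. Single-endpoint power was 73–79%, against about 86% with the interaction. For 150/125/100% the SAP model gave 20.7 instead of 16.6.

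**The case against.** The omission is probably a drafting slip. The Week 26 contrast, the Week 26 hypotheses, the sentence on tests at other visits and the declaration of no change all suggest that the protocol model was intended. That reading is fair, and nothing documents a decision to pool. But SAP 3.0 says the document guides the statistical programming, and a programmer who follows the listed terms will leave the interaction out. Because one interaction is named, the list cannot be read as shorthand for main effects only.

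The effect profiles are assumed, and the fade to zero is the harshest. The documents report a motor benefit (Off time) apparent by Week 4 and persisting to Week 54 in an open-label study, which hints at stability. If the effect is constant, the SAP model is unbiased and more powerful: 95–96% against 85–86%. For a mild build-up of 80/90/100% the estimate falls only to 14.9, and power stays at 87–92%. On the trial's own criterion of at least one endpoint under Hochberg, the 50/75/100% case costs less: about 81–88% against 93%. All of this stands. It limits how large the harm is likely to be, but the gain rests on an equal-effects assumption that the protocol did not make.

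The by-visit descriptive summaries and the final-visit ANCOVA in SAP 9.3 could reveal a changing effect. They do not feed the Hochberg test, and the ANCOVA uses the last observation instead of Week 26.

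**Conclusion.** The concern holds. The listed SAP model contradicts the protocol and cannot test the SAP's own Week 26 hypothesis, for either primary endpoint or for the secondaries that reuse it. No other SAP section restores the term. CGI-C and PGIC, analysed by ANOVA, are not affected.

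The contradiction is certain; the numerical harm is conditional. It is nil for a constant effect. Under the assumed shapes it ranges from an estimate of 12.4 instead of 16.6 to rejection of a true Week 26 null in about half of trials or more. These figures assume 40 per arm, SD 24 at each visit and the stated correlations. Missing Week 26 data would move weight further towards the earlier visits. As the text stands, two readings of the plan give different primary P values, so this must be settled before results are known.

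**What to change.** In SAP 9.2, list the fixed effects as treatment, country, visit and treatment-by-visit, with baseline score and baseline-by-visit as covariates. State that the primary contrast is the LCIG minus OMT difference in Week 26 LS means from the treatment-by-visit term. SAP 9.3 should point to that corrected model. If a pooled effect is really wanted, the hypotheses must be rewritten to match, and the change declared and justified in SAP 12.0.

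While editing, settle the separate mismatch between the protocol synopsis, which has site in the model, and Protocol 8.1.3.1, which has country.

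The cost is one line of text and one model term. No extra data are needed, and the sample size is unchanged because it was not derived from the repeated-measures model.

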The Sponsor, in conjunction with the rater training vendor, will determine the minimum rater qualifications for the rating scale. All raters must meet these qualifications prior to participation in the training process. The names and qualifications of all site personnel to be involved in the UPDRS, rating scale administration will be submitted for approval upon site selection. The qualifications of the raters will be verified through the rater training vendor. Qualified raters will be trained and tested for competency and, if they meet established requirements, will be certified. Individual exceptions to these requirements must be approved by the Sponsor via the rater training vendor.

Only those persons who have been trained and certified as raters for this study may rate the subjects. Raters who cannot participate in the initial pre-study certification/training or who become involved in the study at a later time will not be permitted to perform study ratings until they have satisfactorily completed an individualized certification/training program designed by the rater training vendor, approved by the Sponsor, and supervised by the Investigator or his/her designee. It is the responsibility of the Investigator to ensure the raters at his/her site are appropriately trained and certified to administer the selected rating scales. Raters will be reassessed periodically throughout the study.

Blinded Rater Training Requirements

The NMSS and PDSS-2 will be administered by blinded central raters on the respective scales at Randomization, V3. This will serve as the baseline for clinical assessment. They will also administer both scales at Weeks 6, 12, and 26.

It is required that only trained and certified specialists on movement disorders with previous experience using the NMSS scale in advanced PD patients will serve as blinded central raters and administer NMSS and PDSS-2. The blinded raters will not have access to the results of other study assessments or medical records for the subject and will not participate in the care or management of the subject. Each rating is based exclusively on an interview with the subject (and the subject's caregiver when available).

The blinded central rater will complete the NMSS and PDSS-2 at the times indicated in [Table 3](#) with the baseline assessment occurring at Screening Visit 3.

Rater Training Requirements for All Other Secondary Scales

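### If the unstructured MMRM fails to converge, the AR(1) and CS fallbacks pool the variance over visits, so the Week 26 standard error can be wrong in either direction

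*SAP*

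**What the plan says.** SAP 9.2 starts from the most flexible covariance: "The unstructured covariance structure will be used to estimate the within subject variance-covariance structure". Non-convergence is the only trigger for a change. First, "the first order autoregressive (AR[1]) covariance structure will be substituted". Then: "If the model still fails to converge, the compound symmetry (CS) covariance structure will be substituted".

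Inference is model-based: "Satterthwaite's approximation will be used to estimate the denominator degrees of freedom", and "The LS mean and 95% confidence interval obtained from the model will be presented". No heterogeneous-variance structure and no sandwich (empirical) variance is named. Protocol 8.1.3.1 names no covariance structure at all.

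On timing, Protocol 5.3.1.2 says of the blinded raters after baseline: "They will also administer both scales at Weeks 6, 12, and 26". SAP Table 1 gives nominal Days 42, 84 and 182. One visit carries the test: "The primary comparison will be the contrast between LCIG and optimized medical treatment at the Week 26 Visit".

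SAP 9.3 applies the same model to UPDRS Part II, the PDQ-8 summary index and the other change-from-baseline scales. CGI-C and PGIC are analysed there by ANOVA, so this point does not reach them.

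**The concern.** AR(1) and CS each have two parameters: one variance and one correlation. Neither lets the spread of the change scores differ between visits. When treatment effects are free at each visit, the Week 26 estimate depends essentially on the Week 26 data, but under either fallback its standard error is built from a variance averaged over three visits.

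If responses spread out over time, the averaged variance is too small for Week 26 and the P value is too small. If they converge, the P value is too large. That P value goes straight into the Hochberg procedure for NMSS and PDSS-2. If both primaries succeed, the same issue could affect two of the three key secondary endpoints. The documents give no ground for assuming equal variances: the only NMSS SD is from Week 12 of another study, and the PDSS-2 SD is itself an estimate.

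**Working it through.** **Inputs from the documents.** Three post-baseline visits (Weeks 6, 12, 26). Sample size figures from Protocol 8.2 and SAP 4.3: differences 24.8 − 8.2 = 16.6 (NMSS, SD 24) and 13.1 − 4.3 = 8.8 (PDSS-2, SD 12.2), correlation 0.5, 37 per group, 44 per group with baseline carried forward. The mean model is the protocol's (8.1.3.1): "The model will include fixed, categorical effects for treatment, country, visit, and treatment-by-visit interaction". SAP 9.2 does not list the treatment-by-visit term; that is a separate matter.

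**Assumed inputs.** Visit-specific SDs and within-subject correlations appear in neither document, so ranges are used.

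**The plan's own figure.** Simulating the stated assumptions with two-sided t tests and Hochberg gives 90.7% power at 37 per group. At 44 per group with baseline carried forward it gives 91.9% (4 missing per arm) or 90.9% (5 missing). The stated 90% reproduces, and it does not depend on the covariance fallback.

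**Step 1: standard error under a fallback (complete data).**
- True SE = SD26 × √(2/n).
- Model SE = pooled SD × √(2/n), where pooled SD = √[(SD6² + SD12² + SD26²)/3]. This holds for CS. The AR(1) estimate came within 0.03 of it in the patterns fitted.
- Ratio r = pooled SD / SD26. The sample size cancels and only the SD pattern matters, so the same ratios apply to PDSS-2.

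Example, 20/22/24 with n = 37: pooled SD = √[(400 + 484 + 576)/3] = 22.06. Model SE = 22.06 × √(2/37) = 5.13. True SE = 24 × √(2/37) = 5.58. So r = 0.919, about 8% too small.

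**Step 2: true error.** In large samples, true error = 2[1 − Φ(z × r)], with z = 1.960 at 5% and 2.241 at 2.5% (the Hochberg second step).

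| Assumed SDs, Weeks 6/12/26 | Pooled SD | r | True error at 5% | True error at 2.5% |
|---|---|---|---|---|
| 24/24/24 | 24.00 | 1.00 | 5.0% | 2.5% |
| 22/24/26 | 24.06 | 0.925 | 7.0% | 3.8% |
| 20/22/24 | 22.06 | 0.919 | 7.2% | 3.9% |
| 20/24/28 | 24.22 | 0.865 | 9.0% | 5.2% |
| 24/22/20 | 22.06 | 1.103 | 3.1% | 1.3% |
| 28/24/20 | 24.22 | 1.211 | 1.8% | 0.7% |

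These are per-test rates, given that a fallback is in use. For 20/24/28, the 95% interval covers about 91% of the time.

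**Step 3: simulation, complete data, 40 per arm.** Separate runs under the homogeneous fallbacks gave 6.4–7.2% (22/24/26), 8.7–9.3% (20/24/28) and 1.7–1.9% (28/24/20). Unstructured stayed at about 5%.

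**Step 4: simulation with dropout.** REML, 44 per arm, about 15% monotone dropout, 1,500 trials, SDs 20/22/24. Model SE over empirical SE was 0.90 for AR(1) and for CS, with 7.0% rejection for each. Unstructured gave 0.99 and 4.9%. Monte Carlo error is about 0.6 points.

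**Step 5: is it the 6- and 14-week spacing?** With equal SDs and correlation decaying in calendar time, r is 1.00 with complete data. With about 15% dropout, the SE ratio was 0.97 for both AR(1) and unstructured, with 5.5% rejection for both. CS gave 0.96 and 6.1%. Common variance is the driver, not spacing.

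**Step 6: does the remedy hold the level?** ARH(1), heterogeneous CS and heterogeneous Toeplitz gave 3.6–5.6% across the equal, rising and falling patterns (1,500 runs each). An uncorrected sandwich on AR(1) gave 5.3–5.9% in one set of runs. In another, with equal SDs, 80 subjects and dropout, it gave 6.5%, against 5.1% model-based.

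**The case against.** The strongest reply is that the fallback will hardly ever be used. An unstructured 3×3 matrix has six parameters, and about 88 subjects are planned. In 2,000 simulated trials with 80 subjects, 10 countries and about 12% monotone dropout, the unstructured fit never failed. That used a general optimiser rather than PROC MIXED, but it supports the view that the trigger is rare. Sparse domain scores may be less stable, but they lie outside the Hochberg families.

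The visit SDs are also assumptions. The 20/24/28 pattern makes the Week 26 variance 1.96 times the Week 6 variance (784/400), and falling SDs make the test conservative. The SAP offers partial cover too. The ANCOVA on final scores in 9.3 needs no within-subject covariance, and the visit-wise SDs reported under 9.2 would expose a mismatch.

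All of this stands and limits the priority. It does not remove the point: neither the ANCOVA nor the SD table replaces the primary P value, and a pre-specified fallback should be sound when it is needed.

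A reader might also infer that the unequal gaps between visits make AR(1) invalid for Week 26. AR(1) does ignore the gaps, but Step 5 shows almost no effect on the Week 26 standard error.

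**Conclusion.** The point holds in conditional form. If the unstructured model does not converge, AR(1) or CS takes the Week 26 standard error from a variance pooled over three visits. A nominal 5% test would then run at about 7% (SDs 22/24/26), 9% (20/24/28) or 2% (28/24/20). These figures rest on assumed SDs and on a model with treatment-by-visit means.

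Three stronger readings are not supported:
- That the trial's type I error is 7–9%. Those rates apply only after an unlikely event and only for rising SDs.
- That the plan is biased towards LCIG. The error is in the standard error and can go either way.
- That every secondary analysis is exposed. CGI-C and PGIC are not.

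Priority is low: worth fixing because it is cheap, not because the primary result is in doubt.

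**What to change.** In SAP 9.2, place heterogeneous-variance structures between unstructured and the present fallbacks: unstructured, then ARH(1), then heterogeneous CS, with AR(1) and CS kept only as a last resort. ARH(1) and heterogeneous CS each need four parameters on three visits, two fewer than unstructured, so they simplify the fit and still give Week 26 its own variance. Heterogeneous Toeplitz needs five and saves only one.

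If a homogeneous structure is reached, report a small-sample-corrected sandwich standard error alongside the model-based one, and name the correction and the degrees of freedom used with it.

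Two alternatives are not recommended. Spatial power in its standard form keeps one common variance, so it leaves the actual problem untouched. An uncorrected sandwich is mildly liberal at this sample size.

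The cost is one more sentence in the SAP and slightly fewer degrees of freedom than a pooled-variance fallback. It should be settled before database lock, so that no structure is chosen with the data in view. Sample size and stated power do not change.
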